6.4.2 Arm B

6.4.2.1 Standard management

Standard management alone, including refraction testing with provision of glasses and/or specialist contact lens fitting. Glasses or contact lenses to be provided for one or both eyes as required for best corrected visual acuity. Those patients who develop advanced disease and poor spectacle- and lens-corrected visual acuity during the course of the trial will be offered corneal transplantation.

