6.7 Sample Size

We have calculated our sample size as follows:

A difference between the groups in the change in K_{max} of 1.5D from randomisation to 18 months would be viewed as a clinically important difference (based on Wittig-Silva RCT of CXL in adults⁸). A K_{max} increase $>1.5D$ would discriminate a true change in the steepest corneal meridian from measurement artefact and would be visually significant.

A sample size of 46 patients would be required to detect this difference at the 5% significance level with 90% power, assuming a SD of 1.5D. The total sample size has been increased to 60 patients (30/group) to allow for up to 24% loss to follow-up. These estimates are based on 12 and 24 month data reported by Wittig-Silva et al⁸ from which we estimate a pooled SD of the changes of 1.476D.

We expect that on average there will be 10% loss to follow up in both groups. In the study by Wittig-Silva et al, 19% of patients withdrew, crossed over to CXL or had a transplant by 18 months. However, 18% of patients in the control group either received CXL or a transplant. If we specifically adjust the sample size to take account of 10% loss to follow up and up to 20% of the control arm cross-over to CXL or transplant, then our planned total sample size of 60 patients would still provide at least 80% power to detect the clinically important difference. The trial design dictates that children cannot cross over to CXL before 9 months.

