6.10.4 Statistical methods

6.10.4.1 Statistical analysis plan

Patient characteristics at the time of randomisation will be summarised using mean and standard deviation for continuous variables which are approximately normally distributed, median and interquartile range for variables which are not normally distributed, or by frequencies and percentages for categorical variables.

All statistical tests will use a 2-sided p -value of 0.05 unless otherwise specified. All confidence intervals presented will be 95 % and two-sided. A detailed statistical analysis plan will be developed for approval by the Trial Steering Committee and review by the Independent Data Monitoring Committee and finalised before the first statistical analysis of unmasked data. All statistical analyses will be performed using Stata (StataCorp, College Station TX, USA).

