6.10.4.2 Statistical Methods – Outcomes

For each patient the eye with the more advanced keratoconus at the time of randomisation will be defined as the study eye for the primary analysis. The analysis of the primary outcome will be performed using a linear mixed model fitted to all K_{\max} values recorded after randomisation. K_{\max} at randomisation, treatment group, follow-up time, the interaction between treatment and time, and the stratifying variables centre and whether each patient has only one eye eligible will be included as fixed effects and patient will be included as a random effect. This analysis is equivalent to modelling the change in K_{\max} adjusting for K_{\max} values at randomisation. Model assumptions will be assessed, and a logarithmic transformation used if this improves normality of the residuals. The impact of missing K_{\max} values due to the unreliability of topography measurements in patients who are unable to abstain from wearing lenses for 7 days pre-examination following rigid contact lens wear will be mitigated by applying appropriate multiple imputation methods to estimate these values.

Similar linear mixed models will be fitted for continuous outcomes such as uncorrected and best corrected visual acuity measured at randomisation and on more than one occasion during follow-up. Uncorrected and best corrected visual acuity will be measured in logMAR using an ETDRS chart at a distance of 4 metres.

In patients for whom both eyes show progression at the time of randomisation, information from both eyes will be included in a secondary analysis including eye as a fixed effect and patient as a random effect.

Cox survival analysis method will be used to estimate time to Keratoconus progression in each treatment group. Analysis will be stratified by the stratifying variables, centre and whether each patient has only one eye eligible, and patients who do not progress during the course of the trial will be censored at their last follow-up visit.

We will also explore how health and visual disability in children and young patients with keratoconus relate to changes in K_{\max} . CHU9D is a nine-question paediatric generic preference based measure of health outcome which provides a descriptive health profile as well as a utility score and has been validated for self-completion in an adolescent population (11-17 years)¹². CVAQC is a 25-item vision specific questionnaire designed for children¹³.

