Fisher's exact test will be used to compare proportions.

Two sample t tests or Mann Whitney U tests, depending on the distribution of the data, will be used for continuous outcomes measured only at the end of the trial.

6.10.4.3 *Additional Analyses - Subgroup*

An interaction between the number of eyes with progression at randomisation and CXL treatment will be added to the primary efficacy outcome analysis mixed model to investigate whether the effect of CXL differs between patients who had progression at randomisation in one or both eyes.

We will also investigate possible interactions between treatment effect and ethnicity, family history of Keratoconus and atopy as pre-specified subgroup analyses by adding interaction terms to the regression model for the primary outcome.

6.10.5 **Analysis Population and Missing Data**

The primary analysis will be conducted following the intention to treat (ITT) principle where all randomised patients are analysed in their allocated group whether or not they receive their randomised treatment. However, in the event of cross-over from the randomised arm to the other, we will perform two analyses of the primary outcome, the primary ITT analysis and a per protocol analysis. The per-protocol analysis will exclude any information collected from a patient after cross-over. Any cross-over or other treatment deviations will be summarised with reasons.

An ITT analysis will be performed for all secondary outcomes. The impact of missing data will be mitigated against by incorporating information from earlier timepoints using a mixed model approach.

6.11 **Data Monitoring**

6.11.1 **Independent Data Monitoring Committee**

Details of the roles and responsibilities of the Independent Data Monitoring Committee (IDMC), including membership, relationships with other committees, decision making processes, and the timing and frequency of interim analyses (and description of stopping rules and/or guidelines where applicable) are described in detail in the Keralink DMC Terms of Reference (ToR).

6.11.2 **Interim Analyses**

No formal interim analysis is planned, but reports concerning patient safety and key efficacy outcomes will be prepared for review by the Independent Data Monitoring Committee (IDMC) who may request an interim analysis if a report raises concern.

The IDMC will also be asked to review all the assumptions used for the sample size calculation before the end of recruitment.

6.11.3 **Data Monitoring for Harm**

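### Kmax measured after a corneal transplant in the study eye enters the primary ITT model, and the protocol does not settle whether it leaves the per-protocol analysis

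*Protocol*

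**What the plan says.** Protocol 6.10.4.2 fits the primary linear mixed model to all Kmax "values recorded after randomisation". Section 6.10.5 makes the primary analysis intention-to-treat, so that "all randomised patients are analysed in their allocated group whether or not they receive their randomised treatment". Neither section makes an exception for an eye whose cornea has been replaced. The only rule for unusable Kmax is multiple imputation where rigid lens wear prevents reliable topography (6.10.4.2).

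Transplantation is foreseen in two places. Under Arm B, section 6.4.2.1 says: "Those patients who develop advanced disease and poor spectacle- and lens-corrected visual acuity during the course of the trial will be offered corneal transplantation". The power allowance in 6.7 covers "up to 20% of the control arm cross-over to CXL or transplant".

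A per-protocol analysis of the primary outcome is planned "in the event of cross-over from the randomised arm to the other" (6.10.5). It drops only what is collected after cross-over.

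Progression in outcomes (a) and (b) (6.5.2) is a Kmax rise above 1.5 D, confirmed at a later visit, or a change from spectacles to rigid lenses. Transplantation is not listed.

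**The concern.** Section 6.5.2 uses Kmax as the indicator of disease progression, and section 5.1 describes transplantation as replacing the diseased cornea. After a graft, Kmax no longer tracks keratoconus in that eye, yet as written the value enters the primary model. If graft curvature is below the eye's baseline, a control patient whose disease worsened enough to need surgery is recorded as flattened. That pulls the control mean towards or below the CXL mean and biases the comparison against CXL. The reverse is also possible: section 6.11.3.4.4 notes that complications of CXL have in a small number of cases led to transplant, and a grafted CXL eye could record a harm as benefit. With 30 patients per arm, one extreme value shifts the estimate and also inflates its standard error.

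The per-protocol analysis may not help. On the wording of 6.10.5, a grafted control has not moved to the other arm, because transplantation is part of Arm B care.

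**Working it through.** **Inputs.** From 6.7: "A difference between the groups in the change in K_{max} of 1.5D from randomisation to 18 months"; "at the 5% significance level with 90% power, assuming a SD of 1.5D"; 60 patients, 30 per arm; 10% loss; up to 20% of controls crossing over or transplanted. From 6.10.4.1: "All statistical tests will use a 2-sided" level of 0.05. The documents give no post-graft Kmax and no separate transplant rate. The 18% in 6.7 comes from an adult trial and combines CXL with transplant.

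**1. The plan's own figures.** With difference 1.5 D and SD 1.5 D, the two-sample t-test needs 22.02 per arm for 90% power, rounded up to 23, so 46 in total. With 24% loss, 60 × 0.76 = 45.6, which agrees with 46 to rounding. With 10% loss, 30 × 0.9 = 27 per arm. If 20% of controls contribute no difference, the effect is 1.5 × 0.8 = 1.2 D. Power is then 82% (t-test) or 84% (normal approximation), so the claim of at least 80% reproduces. It does so by giving every crossed-over or transplanted control the CXL-arm mean change. A graft that flattens the eye further is outside that allowance.

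**2. Shift from one graft.** Take 27 per arm, CXL mean change 0 D, ungrafted control mean +1.5 D, and an assumed change g in one grafted control. The expected difference is (26 × 1.5 + g)/27.

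**3. Power.** Without a graft, power is 95%. Two calculations with one graft:

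- *18-month t-test on change*, SD 1.5 D, 20,000 simulated trials per scenario.
- *Random-intercept mixed model*, closer to 6.10.4.2: visits at 3, 6, 9, 12, 15 and 18 months; assumed SDs 1.2 D between and 0.9 D within patients (√(1.44 + 0.81) = 1.5); control drift linear to 1.5 D; grafted values from month 15.

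| Assumed change g | Expected difference | Power, t-test | Power, mixed model |
|---|---|---|---|
| 0 D | 39/27 = 1.44 D | 93% | not tabulated |
| -5 D | 34/27 = 1.26 D | 77% | about 81% |
| -10 D | 29/27 = 1.07 D | 40% | about 64% |
| -15 D | 24/27 = 0.89 D | 8% | about 38% |

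The mixed-model figures depend on the variance split and on how time is modelled. One set of 200 simulations per scenario gave 85%, 63% and 42% for -5, -10 and -15 D with categorical time, and 88%, 75% and 55% with linear time.

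**4. Cross-over wording.** Section 6.10.5 defines cross-over as a move to the other randomised arm. Section 6.4.2.1 makes transplantation part of Arm B. On these two, a grafted control stays in the per-protocol analysis. Section 6.7 names transplant alongside CXL as a destination of cross-over, and on that reading the post-graft data come out. The three sections do not resolve it.

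**5. Progression.** Transplantation is offered when lens-corrected acuity is also poor, so an eye in spectacles at entry would normally have met the rigid-lens criterion before any graft. An event already recorded is not undone by a later graft. What can be missed is an eye that met neither criterion first. One example is a study eye already in a rigid lens at entry, which 6.3.1.3 does not exclude outright. Another is a graft between a first Kmax rise and its confirming visit.

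**The case against.** Transplantation belongs to the Arm B strategy, so analysing all values under ITT is a recognised treatment-policy choice, and removing post-graft values from the primary model would change the estimand. This stands, and the fix leaves the ITT analysis in place.

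Grafts should be rare. Scarring, apex thickness below 400 µ and Kmax above 60 D are excluded at entry (6.3.1.3), follow-up is 18 months, and the 21% transplant figure in 5.1 is an eventual one. This also stands. It lowers the chance of the problem, not its effect if it occurs.

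Detail of this kind often belongs in the SAP, and 6.10.4.2 says model assumptions will be assessed. But the protocol itself fixes the use of all values together with ITT, already gives a rule for one kind of unusable Kmax, and uses cross-over in two senses. Spotting an outlier after unmasking is a weak substitute for a rule set beforehand.

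A reader might go further and infer that the worst control eyes would score as the most improved, that the per-protocol analysis certainly keeps them, or that one graft leaves 8% power. The documents support none of these. They give neither direction nor size for post-graft Kmax; section 6.7 allows the opposite reading of cross-over; and 8% is the extreme of an assumed range under a single-visit t-test, not the planned model.

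**Conclusion.** The point holds in limited form. As written, post-graft Kmax in the study eye enters the primary analysis although it no longer measures keratoconus, and its place in the per-protocol analysis is unresolved. The effect could be bias against CXL if controls are grafted, or in its favour if a treated eye is. One graft among 27 controls costs almost nothing at an assumed change of 0 D (1.44 D, 93% power by t-test). At -5 to -15 D it lowers the difference to 1.26 to 0.89 D, and power to about 81% to 38% under the mixed model or 77% to 8% under the t-test. These figures rest on the assumed post-graft change, the assumed variance components and a graft occurring by month 15. The gap in outcomes (a) and (b) is narrow. A reader might take it that grafted eyes are generally counted as not progressed, but the rigid-lens criterion makes that the exception.

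**What to change.** Before unmasked data are seen:

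1. Reconcile 6.4.2.1, 6.7 and 6.10.5 by stating that, for analysis, a transplant in the study eye counts as cross-over, so that post-graft data leave the per-protocol analysis in both arms.
2. Keep the primary ITT analysis, and pre-specify a supplementary analysis of the primary outcome that treats a study-eye transplant as an intercurrent event and omits post-graft Kmax in both arms. The mixed model then uses that eye's pre-graft visits.
3. Count a study-eye transplant as a progression event in outcomes (a) and (b).

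The cost is one extra analysis and a slightly wider progression definition. These are analysis definitions only; nothing in patient care changes.

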6.4.3 Treatment schedule

Patients randomised to cross-linking will be added to a surgical list following enrolment and a letter will be sent to the patient with confirmation of the surgery date. Patients randomised to CXL will receive treatment no later than 4 weeks following randomisation but as soon as is feasible in all cases.

For participants with both eyes eligible, management of the second eye will be according to the randomised allocation for the first eye, unless there is a specific patient preference not to do so. The eye with the more advanced keratoconus at the time of randomisation will be categorised as the study eye for the primary analysis. Participants with both eyes eligible and who are randomised to CXL, can choose whether to have the procedure on both eyes at the same time. For participants with only one eye eligible at the time of randomisation, if during the course of the study the second eye has progressive keratoconus then management will be according to the randomised allocation.

Those participants with keratoconus progression identified on the basis of clinically significant worsening of vision during the study follow up will be offered further management on a patient-by-patient basis. Those participants who are randomised to CXL but choose not to have the surgery will be managed according to standard care.

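### The per-protocol analysis drops Kmax after cross-over but is fitted with only a patient random effect, so it understates the CXL benefit without cross-over

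*Protocol*

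**What the plan says.** Section 6.10.5 makes ITT primary and adds, in the event of cross-over: "we will perform two analyses of the primary outcome, the primary ITT analysis and a per protocol analysis". The rule for the second analysis is "The per-protocol analysis will exclude any information collected from a patient after cross-over". Values before the switch are kept.

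Section 6.10.4.2 gives the primary-outcome model: a linear mixed model on all post-randomisation Kmax values. Baseline Kmax, treatment, time, treatment by time and the stratifiers "will be included as fixed effects and patient will be included as a random effect". No random slope is stated. The multiple imputation described there covers only Kmax lost because of rigid lens wear.

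Two other sections show who is likely to switch, and how many. Section 6.4.3 offers further management, patient by patient, to "Those participants with keratoconus progression identified on the basis of clinically significant worsening of vision" during follow-up. Section 6.7 allows for "up to 20% of the control arm cross-over to CXL or transplant" and says that a child cannot cross over to CXL before 9 months.

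**The concern.** The natural question for this analysis is what the 18-month difference in Kmax would have been had nobody switched. Removing post-switch values can answer it only if the model predicts what those children would have reached. If switching follows progression, they are among the controls steepening fastest. A random intercept uses a child's earlier level but not the child's own rate of change. The projected control mean at 18 months is then too low, and so is the CXL benefit.

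This is the only analysis that the protocol specifies to deal with cross-over. Readers will tend to take it as the effect freed from cross-over dilution. The shortfall grows with the number of controls who switch because they progressed.

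**Working it through.** **1. The plan's own figures (6.7).** The difference "of 1.5D from randomisation to 18 months would be viewed as a clinically important difference", and 46 patients "would be required to detect this difference at the 5% significance level with 90% power, assuming a SD of 1.5D".
- Normal approximation: n per arm = 2 × (1.96 + 1.2816)² × (1.5/1.5)² = 21.01, so 22 per arm or 44 in total.
- Exact t test: 22 per arm gives 89.97% and 23 per arm gives 91.2%, so 46 is reproduced. Also 60 × 0.76 = 45.6.
- Cross-over case: 30 × 0.9 = 27 per arm, and a diluted effect of 0.8 × 1.5 = 1.2 D (a reconstruction). SE = 1.5 × √(2/27) = 0.408 D, and 1.2/0.408 − 1.96 = 0.98, so power is 83.6% (82.2% by t test). This agrees with the stated minimum of 80%.

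**2. What the random intercept carries forward.** Suppose a control steepens by d dioptres more than the control average over 18 months, in a straight line.
- Switch after the 9-month visit: the mean excess over months 3, 6 and 9 is d × [(3 + 6 + 9)/3]/18 = d/3.
- Switch after the 12-month visit: it is d × [(3 + 6 + 9 + 12)/4]/18 = 0.42d.

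The predicted patient effect is at most about that mean, and shrinkage lowers it further. So at least 58-67% of the child's excess at 18 months is not projected.

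**3. Size by large-sample simulation.** Visits are at 3, 6, 9, 12, 15 and 18 months, the true difference is 1.5 D and the SD of the 18-month change is 1.5 D. The following are assumed, because the protocol does not give them: measurement SD of 0.3-0.5 D; mean changes of +1.0/−0.5 D or +1.5/0 D (control/CXL); the cross-over trigger; and Kmax after cross-over. Entries are the estimated CXL benefit at 18 months, in D.

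| Set of runs | Control cross-over | No deletion | Per-protocol, random intercept | Per-protocol, random slope |
|---|---|---|---|---|
| A: linear slopes, switch on a confirmed rise above 1.5 D, 3,000-6,000 per arm | 19-20% | 1.48-1.53 | 1.25-1.32 | 1.47-1.53 |
| B: slopes make up all or half of the variance in true change, switch on a confirmed rise or by the steepest fifth at 9 or 12 months, 1,500 per arm | 18-20% | 1.47-1.51 | 1.28-1.33 (time categorical), 1.33-1.37 (time linear) | 1.48-1.53 (time categorical) |
| C: noisy trigger resembling a vision-based one | 18% | 1.43 | 1.27 | 1.43 |

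In sets A and B, the shortfall against 1.5 D runs from (1.5 − 1.37)/1.5 = 9% to (1.5 − 1.25)/1.5 = 17%. In set C it is (1.43 − 1.27)/1.43 = 11% of the no-deletion value. At 12% cross-over it was 0.13-0.16 D, and over 8-13% cross-over about 7-11%.

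**4. Cross-check of 2 against 3.** A shortfall of 0.13-0.25 D spread over 20% of controls is 0.65-1.25 D per switching child. If two thirds of d is missed, d is about 1.0-1.9 D, or 0.7-1.3 SD. That is plausible for the steepest fifth.

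**5. Position relative to ITT (set B).** ITT depends on Kmax after the late CXL.

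| Assumed Kmax after late CXL | ITT (D) | Per-protocol compared with ITT |
|---|---|---|
| Steepening halts | 1.23-1.41 | 0.01-0.06 below (confirmed rise, or switch at 12 months); from 0.01 below to 0.07 above (switch at 9 months) |
| Falls by 0.5 D | 1.13-1.34 | 0.03-0.17 above |
| Falls by 1 D | 1.03-1.27 | 0.10-0.28 above |
| Returns to the CXL-arm course | 0.90-1.10 | 0.27-0.40 above |

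**The case against.** **The deletion rule is not itself the error.** This stands: setting post-switch values to missing is acceptable. The fault lies in combining it with the random part of 6.10.4.2. Section 6.10.5 does not restate a model for this analysis, so applying that one is the plain reading but still an inference. The SAP is not among the documents at hand. If it already adds a random slope, the point is met.

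**The trigger is not stated.** Section 6.4.3 speaks of worsening vision and individual management; it names neither CXL nor a Kmax threshold. Progression-driven switching is therefore likely, not certain. The noisy trigger in set C gave the same direction.

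**Twenty per cent is a ceiling.** It includes transplant, which 6.4.2.1 offers within the control arm and which may not count as cross-over to the other arm. Lower rates give the smaller shortfall.

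**The practical weight is modest.** Twenty per cent of 30 is 6 children. With 27-30 per arm the SE is about 0.4 D, so 0.13-0.25 D is roughly 0.3-0.6 of one SE, in a supportive analysis.

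Two stronger readings are tempting, but the protocol does not support them:
- A reader might infer that per-protocol must fall below ITT and so hide the dilution. That happens only if late CXL slows or halts steepening without appreciable flattening, and mainly when the switch follows confirmed progression or comes at about 12 months. In set A, where late CXL only slowed the child's rate or set it to the CXL arm's mean rate, per-protocol was 0.02-0.18 D below ITT. With flattening of 0.5 D or more, or under the reconstructed 1.2 D dilution, it lies above. Section 5.1 cites flattening after CXL in adults, and the protocol has no figure for controls treated late.
- A reader might infer that children who decline CXL are dropped altogether while switching controls keep their early visits. Section 6.4.3 says only that decliners receive standard care. Whether that counts as cross-over is not defined, and no figure is available.

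**Conclusion.** The point holds in a limited form. As written, the per-protocol analysis is biased toward no effect as an estimate of the CXL benefit without cross-over. The shortfall is about 0.13-0.25 D (9-17% of 1.5 D) at 20% control cross-over and about 7-11% at 8-13%. This rests on three assumptions: patient-specific progression that is roughly linear, switching related to progression, and patient as a random effect meaning a random intercept. The switching controls stay in the model up to their switch; only their later values go. Whether the result lies above or below ITT cannot be said from the protocol. The primary ITT analysis and the sample size are not affected. The change is worth making because this is the only specified cross-over analysis and the repair is cheap.

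**What to change.** Keep the rule that sets values after cross-over to missing. Add to 6.10.5, or to the SAP before unmasked data are analysed, that this analysis is fitted with a patient random intercept and a random slope for time, or with visit as a factor and an unstructured covariance. Each child's own course up to the switch then informs the missing 18-month value. Label the result supportive and state the direction of residual bias. In set B the random-slope estimate ranged from 0.02 D below to 0.06 D above its no-deletion value, and the overshoot was largest where only half the variance came from slopes.

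The cost is wording and one extra model fit on data already collected, with no extra patients or visits. The standard error will be somewhat larger, and convergence must be checked with about 60 patients. In simulation the random-slope model converged in all 60 runs at 27 per arm.
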